Appendix 2.8.4. Between-Day Glucose Variability

The notation below is for both between-day and within day glucose variability derivation:

i represents a time point within a time period (a 24-hour period, daytime or nighttime [defined as midnight to 0600])

n represents the number of time points within the time period

k represents a valid CGM day within a visit

m represents number of valid CGM days at a visit

$BG_{k,i}$ represents the glucose value at time point i on day k unless otherwise specified

For variables assessing between-day variability, first determine the variability for each time points across valid CGM days within a visit then average across all time points.

Between-day glucose standard deviation (SD) [Rodbard 2009]:

$$SD = \frac{1}{n} \sum_{i=1}^n SD_i = \frac{1}{n} \sum_{i=1}^n \sqrt{\frac{\sum_{k=1}^m (BG_{k,i} - \frac{\sum_{k=1}^m BG_{k,i}}{m})^2}{m-1}}$$

Between-day glucose coefficient of variation (CV) [Clarke and Kovatchev 2009]:

$$CV = \frac{1}{n} \sum_{i=1}^n CV_i = \frac{1}{n} \sum_{i=1}^n \left(\frac{SD_i}{\frac{\sum_{k=1}^m BG_{k,i}}{m}} \right) \times 100$$

Mean of daily differences (MODD): this parameter is calculated as the mean of absolute differences between glucose values at corresponding time points of consecutive days.

$$MODD = \frac{1}{m-1} \sum_{k=1}^{m-1} \frac{\sum_{i=1}^n |BG_{k+1,i} - BG_{k,i}|}{n}$$

Appendix 2.8.5. Within-day glucose variability

For variables assessing within-day variability, first determine the variability within each valid CGM day, then average across all valid CGM days within a visit.

Within-day glucose SD (Hirsch 2005; Rodbard 2009):

$$SD = \frac{1}{m} \sum_{k=1}^m SD_k = \frac{1}{m} \sum_{k=1}^m \sqrt{\frac{\sum_{i=1}^n (BG_{k,i} - \frac{\sum_{i=1}^n BG_{k,i}}{n})^2}{n-1}}$$

Within-day glucose CV (Clarke and Kovatchev 2009):

$$CV = \frac{1}{m} \sum_{k=1}^m CV_k = \frac{1}{m} \sum_{k=1}^m \frac{SD_k}{\frac{\sum_{i=1}^n BG_{k,i}}{n}} \times 100$$

Inter-quartile range (IQR) [Mazze et al. 2008]:

$$IQR = \frac{1}{m} \sum_{k=1}^m IQR_k = \frac{1}{m} \sum_{k=1}^m (75\text{th} - 25\text{th percentile of all BG values on day } k)$$

The low blood glucose index (LBGI) has been developed to quantitate both frequency and severity of hypoglycemia. The LBGI has been validated as a predictor of severe hypoglycemia. The HBGI quantifies both frequency and severity of hyperglycemia and has been related to HbA1c and risk for hyperglycemia (Kovatchev et al. 2005). Additionally, both the LBGI and high blood glucose index (HBGI) have a high sensitivity to changes in glycemic profiles and control (Kovatchev et al. 2005). Low blood glucose index is a non-negative number that increases as the number of low readings increases. High blood glucose index is a non-negative number that increases as the number of high readings increases.

The LBGI, HBGI, and blood glucose risk index (BGRI) will be derived for each valid CGM day of a visit in the following steps:

Step 1: For each blood glucose (BG [mg/dL]) at the i^{th} time point, compute the following:

$$f(BG_i) = 1.509 \times [(\ln(BG_i))^{1.084} - 5.381]$$

This transforms the BG data using a nonlinear transformation that maps the BG range of 20 to 600 mg/dL to a symmetric interval of $(-\sqrt{10}, \sqrt{10})$

The center of the BG scale is 112.5 mg/dL and is mapped to 0

Step 2: Compute BG risk for each reading

$$rl(BG_i) = 10 \times f(BG_i)^2 \text{ if } f(BG) < 0; \text{ otherwise } rl(BG_i) = 0$$

$$rh(BG_i) = 10 \times f(BG_i)^2 \text{ if } f(BG) > 0; \text{ otherwise } rh(BG_i) = 0$$

Assign the risk of each BG value by applying the above quadratic risk function

Value range from 0 (achieved when BG = 112.5, the center) to 100

Left side of the parabola is risk of hypoglycemia, and the right side is risk of hyperglycemia

Step 3: Compute LBGI and HBGI

$$LBGI = \frac{1}{n} \sum_{i=1}^n rl(BG_i)$$

$$HBGI = \frac{1}{n} \sum_{i=1}^n rh(BG_i)$$

Step 4: Compute BGRI

$$BGRI = LBGI + HBGI$$

The visit averages of LBGI, HBGI and BGRI will be calculated.

Mean amplitude of glycemc excursions (MAGE) (Service et al. 1970, 1987, Baghurst 2011):

Mean amplitude of glycemc excursions is the mean of the excursions between consecutive peaks and nadirs in BG that meet qualifying criteria,

$$MAGE_k = \frac{\sum_{l=1}^p |BG_{k,l} - BG_{k,l-h}|}{p}$$

where,

$BG_{k,l}$ = the low point in consecutive BG time points for the k^{th} day (nadir)

$BG_{k,l-h}$ = the high point in consecutive BG time points for the k^{th} day (peak)

p = the number of qualifying excursions: $|BG_{k,l} - BG_{k,l-h}| \geq 1 \text{ SD}_k$ and that follow the direction of the first qualifying difference within the BG time points for the k^{th} day.

MAGE- and MAGE+ will also be calculated for both negative and positive excursions, in addition to MAGE+/- for all positive and negative excursions combined (Baghurst 2011). The peaks and nadirs will be algorithmically (Baghurst 2011; Approach 1), using a variant that removes the proposed and unnecessary first step of using a smoothing function.

Appendix 2.8.6. Glucose in Target Ranges, Hypoglycemia - or Hyperglycemia

The percentage of time within a glucose range (target, hypo- or hyperglycemia ranges) will be calculated as the number of observations within the specified range divided by the number of

observations in the time interval (eg, 24-hour period) on all valid CGM days at the same visit. The duration (in minutes) within the glucose range will then be calculated as the percentage of time within the glucose range times the length of the period (24 hour, 18 hour, and 6 hour, for the periods of 24-hour, daytime or nighttime, respectively).

For example, if a patient had a total of 13 observations with glucose values ≤ 70 mg/dL (3.9 mmol/L) out of a total of 270 non-missing observations recorded during the 24-hour period across a valid CGM day (with missing observations $< 30\%$ of 288 measures per day), the percentage of time spent in hypoglycemia during the 24-hour period for this patient on this day will be calculated as $13/270 = 4.8\%$. For a visit, the average percentage across all valid CGM days during the visit will be calculated and used for the calculation of the duration (in minutes) with hypoglycemia (glucose value ≤ 70 mg/dL [3.9 mmol/L]) during the 24-hour period for this patient by multiplying the average percentage with 1440.

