Appendix 2. Statistical Analysis Plan for Continuous Glucose Monitoring (CGM)

Continuous glucose monitoring (CGM) will be performed in a subset of patients in Study I8B-MC-ITSB (ITSB) in order to evaluate the 24-hour glucose profile captured with CGM for LY900014 and Humalog, when either is used in combination with basal insulin as part of a multiple daily injection regimen. In 2 of the treatment groups, LY900014 and Humalog will be administered immediately (0 to 2 minutes) prior to each meal in a double-blind manner. A third open-label treatment group consists of LY900014 administered up to 20 minutes after the start of a meal (LY900014 +20). These 3 treatment groups are denoted as LY900014, Humalog and LY900014+20 in the study objectives.

This appendix provides the statistical analysis plan for the CGM addendum I8B-MC-ITSB(3.1). The target range for #3 objective has been changed from “71 to 180 mg/dL” to “70 to 180 mg/dL” to reflect the recommendations set forth in the “Clinical Targets for Continuous Glucose Monitoring Data Interpretation: Recommendations From the International Consensus on Time in Range” (Battelino et al. 2019). Similarly, one of the cut points for #5 objective has been changed from “ ≤ 70 mg/dL” to “ < 70 mg/dL.”

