Appendix 2.2. General Considerations

The Dexcom G6® Continuous Glucose Monitoring System (Dexcom G6) will be used in CGM addendum I8B-MC-ITSB(3.1). Patients who choose to participate in the Study ITSB CGM addendum (3.1) will use the Dexcom G6 system during 2 periods of time, prior to baseline and prior to the 26-week primary endpoint. The Dexcom G6 will be worn for up to 10 consecutive days per period.

The CGM Population includes all randomized patients who have an informed consent for the CGM addendum signed by parent(s)/legal guardian(s) and valid CGM data at baseline (Visit 4) or primary endpoint (Visit 15). Unless otherwise specified, the analyses of the CGM addendum will use the CGM Population. The data collected after permanent discontinuation of investigational product or during days when patients are temporarily off study treatment will be excluded. There will be no multiplicity adjustment.

To ensure that the CGM outcome variables are only calculated from valid CGM days with sufficient data within the 24-hour, the following criterion will be used to determine a valid CGM day: minimum number of measures per day – at least 70% of the total measures (288 measures per day) that are supposed to be obtained. All the CGM derivations are based on the data from the valid CGM days with sufficient data defined above unless otherwise specified.

Patients will be instructed to capture the start time of 3 main meals (morning meal, mid-day meal, evening) when accompanied by prandial insulin dose during each CGM session in the patient CGM diary page. The start time will be used to derive the CGM meal related outcomes for each meal and across all meals. On valid CGM days, the meal related outcomes will also use the 70% cut-point to determine a valid CGM session for the variable derivation. For example, the $iAUC_{0-2hr}$ after the morning meal for a day requires at least 70% of the 24 measures (ie, at least 17 measures) during the 2 hour time window after the start of the morning meal. If the analysis time window covers the start time of the next meal (assuming $TN0$ relative to the start time of the given meal and $TN0 < T$) and the number of non-missing measures within 0 to $TN0$ is greater than 70% of measures within 0 to T , the derivation of the meal related outcomes within 0 to T

will be based on the data from time 0 to *TNO*. Only the first meal of each type per day will be included in derivations

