Appendix 2.5. Secondary CGM Variables and Analysis

The following variables will be derived from the original data collected through the CGM device and will be compared LY900014, LY900014+20 and Humalog at Week 26 using the similar model as the primary analysis in [Appendix 2.4](#):

- incremental AUC 0-2 hours after the start of meals (across all three main meals)
- duration (in minutes) and percentage of time with glucose values between 70 and 180 mg/dL (3.9 and 10.0 mmol/L) (both inclusive) during daytime (defined as 0600 to midnight), normalized to a 24-hour period
- average glucose excursions 0 to 1 hour after the start of meals (across all 3 main meals)
- average glucose excursions 0 to 2 hours after the start of meals (across all 3 main meals)
- average glucose excursions 0 to 3 hours after the start of meals (across all 3 main meals)
- average glucose excursions 0 to 4 hours after the start of meals (across all 3 main meals)
- duration (in minutes) and percentage of time with glucose values <54 (3.0 mmol/L) normalized to a 24-hour period
- duration (in minutes) and percentage of time with glucose values <70 mg/dL (3.9 mmol/L) normalized to a 24-hour period
- duration (in minutes) and percentage of time with glucose values >180mg/dL, (10.0 mmol/L) normalized to a 24-hour period
- blood glucose risk index during daytime (0600 to midnight)

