Appendix 2.8.7. Hypoglycemic/Hyperglycemic Episodes

Hypoglycemic/hyperglycemic episodes are defined as at least 10 consecutive minutes below/above the specified threshold, and determined by 3 or more consecutive CGM values meeting the criterion. For each visit, count the total number of events occurred on the valid CGM days.

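### CGM appendix: a leftover ≤70 mg/dL cut, low-glucose episode counts with no valid-day denominator, and two averaging rules for time in range should be corrected (minor)

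*SAP*

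**What the plan says.** **Averaging.** SAP Appendix 2.8.6 first sets the percentage as readings in the range divided by the "observations in the time interval (eg, 24-hour period) on all valid CGM days at the same visit", which is a pooled ratio. The example in the same section counts 13 low readings "out of a total of 270 non-missing observations recorded during the 24-hour period across a valid CGM day", obtains 4.8%, and continues: "For a visit, the average percentage across all valid CGM days during the visit will be calculated". The minutes follow "for this patient by multiplying the average percentage with 1440". That is an unweighted mean of daily percentages.

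**Completeness.** Under Appendix 2.2 a day is valid with "at least 70% of the total measures (288 measures per day) that are supposed to be obtained". Meal windows have a 70% rule of their own. Daytime (0600 to midnight) and nighttime (midnight to 0600) have none.

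**Cut.** Appendix 2 states that "one of the cut points for #5 objective has been changed from" ≤70 to <70 mg/dL. Table APP.2.1, Table APP.2.2 and Appendix 2.5 follow the change; the last lists "duration (in minutes) and percentage of time with glucose values <70 mg/dL (3.9 mmol/L) normalized to a 24-hour period". The example in Appendix 2.8.6 still uses ≤70, twice. In Appendix 2.9 the lines for time and for number of episodes use <70. The line for the duration of individual episodes carries the ≤ sign next to the words less than.

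**Episodes.** For each visit, Appendix 2.8.7 says to "count the total number of events occurred on the valid CGM days". The sensor is worn for up to 10 days per period, and no minimum number of valid days is given. Appendix 2.9 derives the number of valid days as a separate variable but does not name it as a denominator.

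**The concern.** Appendix 2.8.6 is where a programmer looks to derive time in, below and above range, which are CGM secondary endpoints 3, 5 and 6. Time below 70 mg/dL also feeds the <4% target in Table APP.2.2.

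- Followed literally, the ≤70 cut puts a reading of exactly 70 both in hypoglycemia and in the target range, because that range is 70 to 180 mg/dL inclusive.
- The two averaging rules agree only when every day contributes the same number of readings, and the section does not say which governs.
- An undivided episode count mixes event rate with wear. A difference between arms or visits can then come from wear alone.

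**Working it through.** **Plan's own figure.** 13/270 = 4.815%, which rounds to the stated 4.8%; × 1440 = 69.3 minutes. It reproduces.

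**Completeness bounds.** 0.70 × 288 = 201.6, so a valid day has 202 to 288 readings and up to 86 may be missing. At 288 readings in 24 hours, the 6-hour night holds 72 and the 18-hour day 216.
- Night: 202 is less than 216, so a valid day may have 0 of 72 night readings.
- Daytime minimum: 202 − 72 = 130 of 216 (60%).

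**Effect of the cut.** Assume whole-number readings from a lognormal distribution with mean 160 to 200 mg/dL and CV 38 to 42% (not from the documents). The share at exactly 70 is F(70.5) − F(69.5); the share below 70 is F(69.5).

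| Mean, CV | Share <70 | Share = 70 | Relative increase | Minutes per day |
|---|---|---|---|---|
| 160, 42% | 3.09% | 0.256% | 8.3% | 3.7 |
| 160, 38% | 1.85% | 0.183% | 9.9% | 2.6 |
| 200, 42% | 0.77% | 0.079% | 10.2% | 1.1 |
| 200, 38% | 0.35% | 0.043% | 12.3% | 0.6 |

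**Pooled ratio against mean of daily percentages.** With x low readings out of n on day k, compare Σx/Σn with the mean of x/n.
- *24-hour, two days.* 13/270 and an assumed 29/202: mean of 4.81% and 14.36% = 9.59%; pooled 42/472 = 8.90%. The difference is 0.69 points, or 9.9 minutes.
- *24-hour, worst case over 10 days.* Five days have 202 readings with share c low, and five have 288 with none. The difference is (0.5c − 1010c/2450) × 1440 = 126.4c minutes: 6.3, 12.6 and 25.3 minutes for c = 5%, 10% and 20%.
- *24-hour, simulation.* 50,000 patients with 10 valid days each, n uniform on 202 to 288, daily share mean 4% and SD 4% (all assumed), completeness unrelated to glucose. Mean difference 0.0 minutes, SD 1.9, 95% within 3.8.
- *Night, constructed extreme.* One valid day has 6 night readings, all low; nine days have 72 and none low. The daily rule gives 1/10 = 10%, × 360 = 36 minutes. Pooling gives 6/(6 + 648) = 0.92%, or 3.3 minutes. A valid day with no night readings gives 0/0 under the daily rule.

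**Episode counts.** With the same rate r per day in both arms, the expected counts are r × valid days. An assumed 9 against 7 valid days gives 9/7 = 1.29 with no difference in rate; 9 against 8 gives 1.125.

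**The case against.** A reader might infer that the CGM hypoglycemia results hinge on which sentence of the appendix is followed. The documents do not support that.

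- **The intended cut is clear.** The general rule in Appendix 2.8.6 names no threshold; ≤70 appears only in the illustration. The declared change, both tables, Appendix 2.5 and most of Appendix 2.9 give <70. Either cut would also apply equally to all arms. This stands: the ≤70 is an uncorrected leftover, not an open choice. It still sits in the derivation section and should go.
- **The example may simply spell out the general sentence.** Appendix 2.8.5 uses day-first averaging for within-day variability, so daily averaging is defensible. For 24-hour measures the 70% rule keeps the gap small. This largely stands, and neither estimator is wrong. But the text does not settle which one applies.
- **The large night example touches no listed endpoint.** Endpoint 3 is daytime, endpoints 5 and 6 and the Table APP.2.2 targets are 24-hour, and nighttime appears only among the derived variables. On any valid day, daytime keeps at least 130 readings, so 0/0 cannot arise there. This stands.
- **Episode counts follow one rule, not two.** They are derived variables outside the Appendix 2.5 comparisons, and nothing in the documents suggests that wear will differ by arm. This stands as to weight. However, Appendix 2.2 has all CGM outcome variables summarized by visit and treatment group, so an undivided count would still be shown.

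**Conclusion.** The point holds as a minor one, in three parts.

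1. The ≤70 in Appendix 2.8.6, and its remnant in the episode-duration line of Appendix 2.9, contradict the declared cut of <70. Taken literally they add about 0.6 to 3.7 minutes per day, or 8 to 12% relative, under the lognormal assumptions.
2. Episode counts lack a denominator. The distortion is proportional to any imbalance in valid days; the ratio of 1.29 rests on an assumed 9 against 7.
3. Two averaging rules stand in one section. For 24-hour endpoints the difference is usually a few minutes per day and averages zero if completeness is unrelated to glucose. It becomes large only in sparse sub-day periods.

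The scope is the CGM addendum, a consenting subset analyzed without multiplicity adjustment. The HbA1c primary and gated analyses and the CGM primary outcome (incremental AUC over 0 to 2 hours after meals) do not use these rules.

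**What to change.** - **Cut:** change ≤70 to <70 mg/dL in the Appendix 2.8.6 example and in the episode-duration line of Appendix 2.9.
- **Episodes:** in Appendix 2.8.7 report episodes per valid CGM day, or use a count model with log(valid days) as offset. The valid-day count is already derived in Appendix 2.9.
- **Averaging:** keep one rule in Appendix 2.8.6 and delete the other; either is acceptable. If daily averaging is kept, exclude periods with too few readings, for example by extending the 70% rule to daytime and nighttime.

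The cost is SAP wording and minor programming, with no new data. If the completeness rule is extended, a few sparse periods drop out.

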Appendix 2.8.7. Hypoglycemic/Hyperglycemic Episodes

Hypoglycemic/hyperglycemic episodes are defined as at least 10 consecutive minutes below/above the specified threshold, and determined by 3 or more consecutive CGM values meeting the criterion. For each visit, count the total number of events occurred on the valid CGM days.

Appendix 2.8.8. Maximum Postprandial Glucose

Maximum postprandial glucose was the highest glucose within 4 hours after morning meal/midday meal/evening meal on a valid CGM day.

Maximum glucose excursion was the highest glucose excursion within 4 hours after morning meal/midday meal/evening meal on a valid CGM day.

Time to the maximum glucose was the time to the first maximum glucose value within 4 hours after morning meal/midday meal/evening meal on a valid CGM day.

Appendix 2.9. List of Derived CGM Variables

The following variables will be derived based on valid CGM data and derivation method defined in [Appendix 2.2](#) and [Appendix 2.8](#) respectively.

- Incremental $AUC_{0-1\text{hour}}$, $AUC_{0-2\text{hours}}$, $AUC_{0-3\text{hours}}$, $AUC_{0-4\text{hours}}$ after the start of morning meal, midday meal, evening meal and all three meals during each CGM section up to 10 days
- Average glucose excursion 0 to 1, 2, 3, 4 hours after the start of morning meal, midday meal, and evening meal and all three meals during each CGM section up to 10 days
- Maximum glucose excursion within 4 hours after the start of morning meal, midday meal, evening meal and all three meals
- Maximum glucose within 4 hours after the start of morning meal, midday meal, evening meal and all three meals
- Time to the maximum glucose within 4 hours after the start of morning meal, midday meal, evening meal and all three meals

- Area under the curve for a 24-hour, daytime and nighttime period
- Area under the curve during the 1, 2, 3, 4 hours after the start of morning meal, midday meal, evening meal and all three meals corresponding to above iAUC
- Between-day glucose variability during a 24-hour, daytime and nighttime period
 - standard deviation
 - coefficient of variation
 - mean of daily differences
- Within-day glucose variability during a 24-hour, daytime, nighttime period and 0-4 hour during morning meal, midday meal, evening meal and all three meals
 - standard deviation
 - coefficient of variation
 - Inter-quartile range
 - low blood glucose index
 - high blood glucose index
 - blood glucose risk index
 - mean amplitude of glycemic excursions (MAGE-, MAGE+ and MAGE+/- combined)
- Duration (in minutes) and percentage of time with glucose values within target range 70 to 180 mg/dL (3.9 and 10.0 mmol/L), both inclusive for a 24-hour, daytime and nighttime period
- Duration (in minutes) and percentage of time with glucose values within target range 70 to 180 mg/dL (3.9 and 10.0 mmol/L), both inclusive for 0-1, 0-2, 0-3, 0-4 hours during morning meal, midday meal, evening meal and all meals
- Duration (in minutes) and percentage of time with glucose values within target range 70 to 140 mg/dL (3.9 and 7.8 mmol/L), both inclusive for a 24-hour, daytime and nighttime period
- Duration (in minutes) and percentage of time with glucose values within target range 70 to 140 mg/dL (3.9 and 7.8 mmol/L), both inclusive for 0-1, 0-2, 0-3, 0-4 hours during morning meal, midday meal, evening meal and all meals
- Duration (in minutes) and percentage of time with glucose values within target range 54 to 69 mg/dL (3.0 and 3.8 mmol/L), both inclusive for a 24-hour, daytime and nighttime period
- Duration (in minutes) and percentage of time with glucose values within target range 181 to 250 mg/dL (10.1 and 13.9 mmol/L), both inclusive for a 24-hour, daytime and nighttime period
- Duration (in minutes) and percentage of time with glucose values <54 and (less than) 70 mg/dL (3.0 and 3.9 mmol/L) for a 24-hour, daytime and nighttime period
- Number of hypoglycemic episodes, defined as at least 10 consecutive minutes < 54 and <(less than) 70 mg/dL (3.0 and 3.9 mmol/L) during up to 10 valid CGM days
- Duration (in minutes) and percentage of time with glucose values >180 and >250 mg/dL (10.0 and 13.9 mmol/L) for a 24-hour, daytime and nighttime period
- Number of hyperglycemic episodes, defined as at least 10 consecutive minutes >180 and >250 mg/dL (10.0 and 13.9 mmol/L) during up to 10 valid CGM days

- Ambulatory Glucose Profile for 0 to 4 hours after the start of morning meal, midday meal, evening meal and all meals
- Ambulatory Glucose Profile for the 24-hour window
- Ambulatory Glucose Profile at individual patient level
- Duration (in minutes) of each individual hypoglycemic episode defined as at least 10 consecutive minutes < 54 and \leq (less than)70 mg/dL (3.0 and 3.9 mmol/L)
- Duration (in minutes) of each individual hyperglycemic episode defined as at least 10 consecutive minutes >180 and >250 mg/dL (10.0 and 13.9 mmol/L)
- Number of valid CGM days for each visit

Leo Document ID = ae510c0a-e789-4013-8b32-b69df934b333

Approver: PPD

Approval Date & Time: 20-Jan-2021 22:13:24 GMT

Signature meaning: Approved
